#### Option for Cross-Over

Participants who progress to active target organ disease or whose existing target organ disease progresses (assessed by the Investigator and Sponsor Medical Monitor and based on the criteria in [Appendix 8](#)) between Day 29 and Week 10 will be considered to have experienced progression and will have the option to be crossed over to the alternate treatment arm.

Participants can cross over before Day 29 only if they progress with target organ disease as adjudicated by the Adjudication Committee. For potential cases of premature cross-over (ie, prior to Day 29), participants will be expected to have received both infusions of study treatment before evaluation by the Adjudication Committee. Cross-over participants will receive the alternate treatment to which they were originally randomized, posoleucel or placebo

[REDACTED] infusions separated by [REDACTED]), but study treatment will remain blinded. Participants must meet the following eligibility criteria to cross-over: participant must not have evidence of acute GVHD Grade 3 or higher (Exclusion Criterion 1), must not be receiving ongoing therapy with high-dose systemic corticosteroids  $>0.5$  mg/kg/day prednisone or equivalent unless approved by Medical Monitor (Exclusion Criterion 2), and must not have experienced a severe infusion-related reaction (Grade  $\geq 3$ ) with the prior doses of study treatment (posoleucel or placebo).

If the participant receives any antiviral drugs in violation of the protocol during the study, that participant will be included in the primary analysis, but will not be eligible for cross-over. Follow-up will be continued for safety and persistence of the virus specific T cells (VSTs).

Participants must meet all of the cross-over eligibility criteria by Week 10 of the Primary Study Period to enter the Cross-Over Period. A new baseline (Day 1' of the Cross-Over Period) will be established at the time of the first cross-over infusion. At Day 29' of the Cross-Over Period, participants will be assessed for clinical and virologic response. The participants will then have 20 weeks of safety follow-up, for a total duration of 24 weeks for the Cross-Over Period. The maximum study duration for participants who cross over is 34 weeks, including up to 10 weeks in the Primary Study Period and 24 weeks in the Cross-Over Period.

Participants who cross over are not eligible to receive treatment for recurrence (described below).

---

---

### Recurrence

Participants who demonstrate viral clearance by Day 29 of the Primary Study Period but later exhibit a clinically significant recurrence of AdV viremia (ie,  $\geq 10,000$  copies/mL AdV DNA at the central laboratory) and/or progression of or to active organ disease, will be eligible for an additional dose of the last received therapy (posoleucel or placebo) for recurrence prior to 20 weeks. These participants will continue to have safety follow-up for an additional 20 weeks after administration of the additional dose. The visit in which the participant receives the additional dose for recurrence should mimic the assessments performed on Day 15. Participants who receive an additional dose for recurrence will be monitored using the schedule as specified in the Primary Study Period schedule of events starting at the Week 5 visit, which should occur 1 week after infusion of the additional dose. This applies even if the participant completed any of these visits prior to receiving the additional dose.

A participant is considered to have completed the study if he/she has completed the Week 24 visit of the Primary Study Period (for participants who do not cross over) or the Week 24' visit of the Cross-Over Period (for participants who cross over). Participants who have a recurrence and receive a third dose are considered to have completed the study once they have completed their 20 Week safety follow up following their third study dose.

The end of the study is defined as completion of the final visit for the final participant.

---

---

## Oversight Committees

An independent Data and Safety Monitoring Board (DSMB) will be convened for this study to routinely monitor participant safety and evaluate prespecified interim analyses for futility and sample size re-estimation (SSRE).

An independent and blinded Adjudication Committee will adjudicate progression from AdV viremia to target organ disease and progression of AdV target organ disease during the study.

## **Assessment Overview**

Viral load of AdV will be measured at the central laboratory at each visit from blood and stool samples and at Day -21 to -1 and Day 29 from nasopharyngeal swab. Blood specimens collected should be analyzed by the central laboratory for screening purposes, however, local laboratory results available up to 5 days prior to and/or during screening will be acceptable to determine eligibility. For the inclusion criterion requiring two consecutive and rising AdV viremia results exceeding 1,000 copies/mL, the two consecutive viremia results used to determine eligibility must have been assayed at the same laboratory, preferably the central laboratory however, local lab results are also acceptable (with Medical Monitor approval). This process is expected to expedite the randomization and dosing of participants whose clinical status may rapidly deteriorate. A central laboratory blood sample must be collected prior to dosing on Day 1. All study analyses will continue to be performed using viral load data from the central laboratory.

Participants will be followed weekly for viremia and viral load in the stool while symptomatic. For participants who require intubation and/or undergo bronchoscopy with bronchoalveolar lavage (BAL), a sample of BAL fluid should, when possible, be obtained for AdV viral load determination at the central laboratory. For participants who develop symptoms and/or signs of possible AdV-associated neurological disease, and whose treating physician determines that laboratory evaluation of cerebrospinal fluid (CSF) for diagnostic and/or monitoring reasons is clinically indicated, CSF samples for AdV viral load determination should, when possible, be sent to the central laboratory. In all cases, BAL and CSF samples required for routine clinical care of the patient take precedence over these study-related evaluations.

The presence or absence of abnormalities consistent with lower respiratory tract infection on chest X-ray and/or CT scan as assessed by the local radiologist should be documented at screening (obtained no more than 10 days prior to dosing) and at Day 29 ( $\pm 3$  days). If no routine clinical radiological imaging of the chest is available at either of these timepoints, a chest X-ray should be obtained (chest CT scan is not a study-mandated procedure; however, the results of chest CT scan[s] performed as part of a participant's standard clinical care may be used for the purposes of the study). For those participants who cross over, chest imaging as described above should be documented within 7 days prior to Day 1' of the Cross-Over Period and at Day 29' ( $\pm 3$  days) of the Cross-Over Period. If the Day 29 imaging from the Primary Study Period falls within the 7-day window prior to cross over, this imaging need not be repeated prior to the participant entering the Cross-Over Period (ie, the Day 29 imaging will serve as the baseline imaging for the Cross-Over Period). All chest X-rays and/or CT scans will also be submitted for central reading, which will be used for analysis purposes.

For evaluation of potential renal, urinary tract, and pancreatic manifestations of AdV infection, a urinalysis (dipstick and microscopy) will be obtained at the local laboratory at Day 1 and Day

---

---

29, and serum amylase and lipase levels will be included in the clinical chemistry evaluations at the central laboratory.

Blood samples will be obtained from all participants for the measurement of posoleucel cell persistence through Week 24.

Repeat or unscheduled samples may be taken based on symptoms, for safety reasons, or for technical issues with the samples.

Safety assessments will include adverse event (AE) monitoring, clinical laboratory assessments, physical examinations, vital sign measurements, and 12-lead electrocardiograms (ECGs).

Additional safety assessments may be performed throughout the duration of the study if clinically indicated.

AEs of special interest (AESIs) include the following:

- Acute or chronic GVHD
- CRS
- Infusion-related reactions (IRRs)
- Graft failure and rejection

---

#### **DOSAGE FORMS AND ROUTE OF ADMINISTRATION:**

Posoleucel will be frozen in a cryopreservation medium containing [REDACTED]

[REDACTED]  
[REDACTED]

Posoleucel will be supplied in [REDACTED] cryovials at a concentration of [REDACTED]

[REDACTED]

Placebo is a [REDACTED]. Upon thaw, under normal light conditions without magnification, both posoleucel and placebo are clear straw-colored liquids.

Posoleucel is to be administered at a fixed cell dose based on weight, as [REDACTED] sequential infusions separated by [REDACTED]

Dose # (Study Day)	Criteria
Dose 1 (Study Day 1/ Study Day 1')	Dose levels for all infusions will be as follows: 

• [REDACTED] [REDACTED]

• [REDACTED]

• [REDACTED] [REDACTED]

• [REDACTED]

Dose 2 (Study [REDACTED] [REDACTED])	All participants will receive a 2 nd dose based on response after the 1 st dose: 

• If AdV viral load decrease from baseline is <math>\geq 0.5 \log_{10}</math> copies/mL AdV DNA at Days 8 or 11/Days 8' or 11', the participant will receive a second dose with the same VST line or placebo lot as the first dose,

• If AdV viral load decrease from baseline is <math>< 0.5 \log_{10}</math> copies/mL AdV DNA at Days 8 or 11/Days 8' or 11', the participant will receive a second dose with a new VST line from a different donor or placebo from a different lot.

---	---

For participants who receive an additional dose for recurrence, the additional dose will be from the same VST line or placebo lot and include the same number of cells as the second dose. An additional dose for recurrence can only be administered after Day 29 of the Primary Study Period (the primary endpoint), but prior to 20 weeks. Participants who receive an additional dose for recurrence are not eligible for subsequent cross-over, and participants who have previously entered the Cross-Over Period are not eligible for a subsequent additional dose.

Participants who have experienced new onset of GVHD, worsening of GVHD, or a Grade  $\geq 3$  IRR will be excluded from redosing with additional doses of blinded study treatment. Reference Section 8.1 for Discontinuation of Study Treatment for details.

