#### Recurrence

Participants who demonstrate viral clearance by Day 29 of the Primary Study Period but later exhibit a clinically significant recurrence of AdV viremia (ie,  $\geq 10,000$  copies/mL AdV DNA at the central laboratory) and/or progression of or to active organ disease, will be eligible for an additional dose of the last received therapy (posoleucel or placebo) for recurrence prior to 20 weeks. These participants will continue to have safety follow-up for an additional 20 weeks after administration of the additional dose. The visit in which the participant receives the additional dose for recurrence should mimic the assessments performed on [REDACTED] Participants who receive an additional dose for recurrence will be monitored using the schedule as specified in the Primary Study Period schedule of events starting at the Week 5 visit, which should occur 1 week after infusion of the additional dose. This applies even if the participant completed any of these visits prior to receiving the additional dose.

A summary of the study design is shown in [Figure 1](#).

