For participants whose AdV viral load as determined by the Central Laboratory has decreased  $\geq 0.5 \log_{10}$  copies/mL AdV DNA between Day 1 and Day 8 or 11, the second dose will be from the same VST line/placebo lot as the first dose. When possible, the Day 11 value should be used to make this determination; however, if a Day 11 value is not available, the Day 8 value can be used. For participants whose AdV viral load has decreased  $<0.5 \log_{10}$  copies/mL AdV DNA between Day 1 and Day 8 or 11, the second dose will be with a new VST line from a different donor or placebo from a different lot. When possible, the Day 11 value should be used to make this determination; however, if a Day 11 value is not available, the Day 8 value can be used. In that case, the VST line chosen for the participant's second infusion will be the VST line with the next-best match according to the CytoMatch hierarchy as described above and will come from a different donor than the first VST line infused, while maintaining a threshold of at least 2 HLA allele matches between the VST line and the virus-infected recipient. The choice of second dose for participants who enter the Cross-Over Period will use the same criteria (with AdV viral load assessment on Day 11' [or Day '8, if Day 11' value is not available] to support the second dose on Day 15').

In the unlikely event that a suitable VST line for the second infusion cannot be identified in the bank, a second dose of the first VST line infused will be substituted for the participant's second infusion.

For participants who receive an additional dose for recurrence, the additional dose will be from the same VST line or placebo lot and include the same number of cells as the second dose. An additional dose for recurrence can only be administered after Day 29 of the Primary Study Period (the primary endpoint), but prior to 20 weeks. Participants who receive an additional dose for recurrence are not eligible for subsequent cross-over, and participants who have previously entered the Cross-Over Period are not eligible for a subsequent additional dose.

Once the lots of drug product have been selected, the treating physician will review and approve documentation that accompanies the drug product shipment prior to dose administration.

Randomization of patients to posoleucel versus placebo will occur only after VST line matching and selection has been confirmed (to satisfy inclusion criteria).

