#### 7.2 Dose Modification

No dose modifications are permitted. Reference Section 8.1 for Discontinuation of Study Treatment Criteria.

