# **8 DISCONTINUATION/WITHDRAWAL CRITERIA**

## **8.1 Discontinuation of Study Treatment**

Participants will be discontinued from study treatment if any of the following criteria are met:

- Development of Grade 3 or higher acute GVHD or a Grade 3 to 4 non-hematologic adverse event between the first and any subsequent dose of posoleucel or placebo that is considered related to study treatment. If this occurs, the participant's toxicities will be followed until resolution or until the participant's participation in the study ends.
- Receipt of any other hematopoietic stem cell product.
- Receipt of therapy for relapse of the participant's primary malignancy.
- Occurrence of Grade 3 or 4 CRS that persists beyond 72 hours. If this occurs, the participant's toxicities will be followed until resolution or until participation in the study ends.
- Occurrence of any medical condition or circumstance that exposes the participant to substantial risk.
- Any SAE, clinically significant adverse event, severe laboratory abnormality, intercurrent illness, or other medical condition that indicates to the Investigator that continued dosing of study treatment is not in the best interest of the participant.
- Pregnancy.
- Requirement for prohibited concomitant medication.
- Participant (or parent or legal guardian) chooses not to receive any further doses of study treatment.

If any of the above criteria are met, every effort should be made to keep the participant in the study and continue follow-up.

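### The synopsis bars redosing after any new or worsening GVHD, but Section 8.1, which it cites, names only Grade 3 or higher acute GVHD

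*Protocol*

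**What the plan says.** In the protocol synopsis, Dosage Forms and Route of Administration, a paragraph on the additional dose for recurrence is followed by a separate sentence. It states that "Participants who have experienced new onset of GVHD, worsening of GVHD", or a Grade 3 or higher infusion-related reaction, "will be excluded from redosing with additional doses of blinded study treatment. Reference Section 8.1 for Discontinuation of Study Treatment for details". The infusion reaction is graded; the GVHD is not.

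Section 8.1 lists the criteria for stopping study treatment. One of them names GVHD: "Development of Grade 3 or higher acute GVHD or a Grade 3 to 4 non-hematologic adverse event between the first and any subsequent dose", with a closing qualifier that the event is judged related to study treatment. The other criteria do not mention GVHD. Among them is an Investigator-judgment criterion covering any "other medical condition that indicates to the Investigator that continued dosing of study treatment is not in the best interest of the participant".

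Three other places in the protocol body bear on redosing:

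- Section 5.1 (Recurrence) says that qualifying participants "will be eligible for an additional dose of the last received therapy (posoleucel or placebo) for recurrence prior to 20 weeks", with no GVHD condition.
- Section 7.1 repeats the synopsis recurrence paragraph, including "An additional dose for recurrence can only be administered after Day 29 of the Primary Study Period", but not the GVHD sentence that follows it in the synopsis.
- Section 7.2 states no GVHD rule and directs the reader onward: "Reference Section 8.1 for Discontinuation of Study Treatment Criteria".

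**The concern.** A summary sentence that sends the reader to a section for details should agree with that section. Here the synopsis states a mandatory exclusion without a GVHD threshold, and the cited section sets a threshold and limits it to acute disease. A site working from the synopsis would exclude a participant automatically. A site working from Sections 5.1, 7.1 and 8.1 could reach a case-by-case decision on the same participant.

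The event is not remote. Section 3.3.2 names GVHD among the main potential risks, and Section 9.2.6 makes new or worsening acute and chronic GVHD an event of special interest. Exclusion Criterion 1 keeps out only acute GVHD of Grade 3 or higher, so a participant can enter with lower-grade disease and worsen within the range where the two texts differ. At stake is uniform application of a safety rule, and a reader's ability to tell from the study report which rule governed.

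**Working it through.** No arithmetic applies. The check sets the current texts side by side, using the acute grades I to IV and the chronic severity categories in Appendix 6. The amendment log describes superseded wording and is not used.

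| Participant's event | Synopsis, Dosage Forms | Section 8.1 |
|---|---|---|
| New or worsening acute GVHD, Grade III or IV | Excluded | Named criterion (subject to how the relatedness qualifier is read) |
| New acute GVHD of Grade I or II, or worsening from I to II | Excluded | Not named; stopped only if another criterion applies |
| New or worsening chronic GVHD that is a related Grade 3 to 4 non-hematologic adverse event | Excluded | Caught by the adverse-event part of the same bullet |
| Any other new or worsening chronic GVHD | Excluded | Not named; stopped only if another criterion applies |

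**Where they differ.** The second and fourth rows. The other Section 8.1 criteria that could reach them are general: a condition exposing the participant to substantial risk, the Investigator's view of the participant's best interest, a need for prohibited medication, or the participant's own choice. None amounts to an automatic exclusion at any grade.

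**Relatedness.** The synopsis sentence has no such condition. In Section 8.1 the qualifier closes a bullet that lists both GVHD and adverse events. Whether it attaches to the GVHD limb is not clear from the grammar. If it does, unrelated Grade III or IV acute GVHD is a further point of difference.

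**Whether the body resolves it.** It does not. Section 7.1 reproduces the recurrence paragraph and stops before the GVHD sentence. Section 5.1 gives no GVHD condition. Section 7.2 leads back to Section 8.1.

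**Which infusions.** The sentence follows the recurrence paragraph, which reserves the phrase for the recurrence dose and treats cross-over as something separate. The narrow reading, recurrence dose only, is therefore the natural one, and the difference from Section 8.1 holds on that reading. The wording could also be taken to reach the second dose or cross-over infusions, and the protocol does not say.

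**Effect on the analysis.** The SAP's mITT population (Section 3.2.2) requires only one dose, and Section 3.4.2 keeps data collected after treatment discontinuation. Neither these nor the sample-size assumptions refer to the redosing rule.

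**The case against.** The best reply is that the two texts can be applied together. Section 8.1 says when treatment must stop; the synopsis adds a further limit on redosing; a site that obeys the synopsis breaches nothing in Section 8.1. Alternatively, the synopsis is a summary and Section 8.1 supplies the specifics. Each reading is coherent, but they give opposite answers for a participant with new Grade II acute GVHD, and the protocol does not say which applies. So the reply explains how the texts could coexist without removing the need to reconcile them.

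Three stronger readings that a reader might infer are not supported.

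- *All chronic GVHD falls outside Section 8.1, or is left there to judgment alone.* The same bullet covers related Grade 3 to 4 non-hematologic adverse events, which could capture severe chronic GVHD, and not every general criterion turns on the Investigator's judgment.
- *Every silent recurrence passage is a separate contradiction.* Of five places that describe the recurrence dose (synopsis Recurrence, synopsis Dosage Forms, Sections 5.1 and 7.1, and SAP Section 2.2.1), only one carries the exclusion. That count measures repetition. Those passages do not restate other bars either, and Section 8.1 already reaches any subsequent dose, so the silence is an omission.
- *The cross-over criteria conflict with the synopsis.* They require that the "participant must not have evidence of acute GVHD Grade 3 or higher (Exclusion Criterion 1"), which would differ from the synopsis only if its sentence is meant to cover cross-over infusions. The text leaves that open, and its position favors the narrower reading.

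**Conclusion.** The inconsistency is real and lies in current text: the synopsis exclusion is broader than the section it cites. The gap consists of new or worsening acute GVHD below Grade 3, and chronic GVHD that is not a related Grade 3 to 4 non-hematologic adverse event. It holds even if the synopsis sentence covers the recurrence dose alone.

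The size in participants cannot be derived from the documents. A reader might infer that sites did treat similar participants differently; the documents show only that they could have. The severity is minor. The SAP introduction says the study was terminated for futility, without saying whether any dosing continued, and the SAP already plans to report discontinuation reasons (Section 3.3.1) and GVHD severity (Section 3.5.2). What those tables cannot show is which redosing rule lay behind them.

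**What to change.** Reconcile the synopsis sentence with Section 8.1 so that both state one GVHD condition: the grade, whether acute, chronic or both, and whether relatedness is required. Name the infusions it covers. Carry the result into the synopsis Recurrence paragraph and Sections 5.1, 7.1 and 7.2. State expressly whether cross-over infusions are included; if they are, also align the cross-over criteria in the synopsis, Section 5.1 and footnote 3 of Table 2. No view is taken on what the condition should be.

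If dosing has ended, one statement in the study report of the rule actually applied is enough.

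The cost is a text correction, plus a clarification to sites if any dosing remains. Sample size and analysis do not change.
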